Many vaping companies present their products as nicotine free and as being a safe and non-addictive way of smoking. From commercials to online ads, consumers are being told that this product is free from the smell of cigarettes, reusable, much cheaper, and even healthier than traditional cigarettes. This information can be very deceiving and persuasive to the young mind.

This program titled, “To Vape or Not to Vape”, will provide education to adolescents and young adults about the potential risk of vaping in an effort to assist with lowering the usage rates within the population. Content will include information about current statistics, potential short-term and long-term side-effects, and healthy alternatives for dealing with stress and peer-pressure. We anticipate that this program will increase this population’s knowledge about the risks of vaping products, and deter them from future use of the products. Effectiveness of this program will be measured by pre and post-tests.

**1.2.** Aim(s)/Objective(s)

The overall goal of this study is to increase knowledge of vaping and its associated risks. This study will find the patterns of vaping, and how it all started among adolescents. We want to know if students are aware of the serious and long term effects of vaping.

The objectives are:

1. To provide at least 100 middle school and high school students with anti-vaping education.
2. To provide at least 40 college students with anti-vaping education.
3. To improve the overall knowledge of vaping statistics and side effects as measured by a pre and post-test. The pre-test will be the baseline measurement. The post-test will be the measure of effectiveness. Out of the 10 questions on the post-test, the goal is to have the students answer at least 8 out of the 10 questions correctly.
4. To decrease the percentage of students who say that they are likely to vape in the future.

The program will be going to middle school, high school, and college campuses in the Dallas-Fort Worth (DFW) area to speak with students about vaping. The program will be implemented by community outreach, as the students will be presented with information about vaping and the resources necessary to prevent or stop vaping. This program will present the students with a 35-minute curriculum that is listed below. The purpose of this study is to relay

and publish data that will support education about vaping and the many health risks associated with vaping products.

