#### **1.4.1.** Primary Hypothesis

By increasing the awareness of vaping products, the number of vape users in teens and young adults will decrease by 5%. The students that participate in this program will obtain the knowledge of risk and side effects from smoking tobacco,

and the use vaping products. The program's goal will be measured by a pre and post survey.

**1.4.1.** Secondary Hypothesis

This program will decrease the individual's likelihood of vaping in the future.

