**2. OBJECTIVES AND STUDY OUTCOME MEASURES**

**2.1.** Study Objectives

**2.1.1.** Primary Objective(s)

The primary objective for this program is to obtain an understanding and gather information on the percentage of vape users in teens and young adults. This study will include at least 100 individuals, as this will allow us to determine why vaping is so prominent, what causes individuals to be attracted towards this habit, and determine why there is an increasing rate of vaping.

**2.1.2.** Secondary Objective(s)

The secondary objective for this program is to prevent those who do not vape to not begin to partake in this habit and to reduce the percentage pf the target population who are currently vaping, by increasing their knowledge on the dangers of vaping by 10%.

**2.2.** Study Outcome Measures

**2.2.1.** Primary Outcome(s)

We will obtain the percentage of vape users and their reasons for vaping from information gathered from pre-test (Appendix C). Within 6 months, we hope to see a decline in the usage of vapes in the DFW area.

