## Appendix B: Data Collection Tool

## Excel Spreadsheet: Pre-Test

## Excel spreadsheet: Post-Test

## Appendix C

### Pre-Test

1. Do you or have you ever smoked tobacco cigarettes?
  - a. Yes, I currently smoke
  - b. Yes, I smoked in the past
  - c. No, I never smoked
2. Do you or have you ever used a vape pen, e-cigarette, or other vaping products?
  - a. Yes, I currently use these products
  - b. Yes, I have tried these products in the past
  - c. No, I never used these products
3. How often do you vape?
  - a. Everyday
  - b. 3 to 5 times a week
  - c. Once a week
  - d. Few times a month
  - e. Never
4. How long have you been vaping and/or using tobacco products?
  - a. Less than 3 months ago
  - b. 6 months ago
  - c. About 1-2 years ago
  - d. More than 2 years ago
  - e. I never have
5. Using vaping products will help you stop smoking cigarettes?
  - a. True
  - b. False
6. Using vaping products may cause harm to my health?
  - a. True
  - b. False
7. By using vaping products, I am more likely to smoke cigarettes in the future.
  - a. True
  - b. False
8. There are currently \_\_\_\_ million students that use vaping products
  - a. 1 million
  - b. 3.5 million
  - c. 8 million
  - d. 5.3 million
9. Students who vape are \_\_\_\_ more likely to begin smoking cigarettes
  - a. twice

b. four times  
c. five times  
d. ten times

10. There are at least \_\_\_\_ confirmed vape related deaths as of January 21st, 2020  
a. 15  
b. 35  
c. 60  
d. 2

11. People vape because \_\_\_\_  
a. It helps them to relax  
b. Their friends or family vape  
c. They like the taste of it  
d. They think it is safer than tobacco cigarettes  
e. All the above

12. I feel pressured to vape.  
a. Yes  
b. No  
c. Sometimes

13. Effects that vaping has on my body are \_\_\_\_  
a. Decreased brain development  
b. Problems with breathing  
c. Increase heart rate  
d. Higher chance of developing cancer  
e. All the above

14. How likely are you to use vaping products?  
a. Not at all  
b. Not sure  
c. Very likely  
d. I already vape

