## Appendix C

### Post-Test

1. Using vaping products will help you stop smoking cigarettes?
  - a. True
  - b. False
2. Using vaping products may cause harm to my health?
  - a. True
  - b. False
3. By using vaping products, I am more likely to smoke cigarettes in the future.
  - a. True
  - b. False
4. There are currently \_\_\_\_ million students that use vaping products
  - a. 1 million
  - b. 3.5 million
  - c. 8 million
  - d. 5.3 million
5. Students who vape are \_\_\_\_ more likely to begin smoking cigarettes
  - a. twice
  - b. four times
  - c. five times
  - d. ten times
6. There are at least \_\_\_\_ confirmed vape related deaths as of January 21st, 2020
  - a. 15
  - b. 35
  - c. 60
  - d. 2
7. People vape because \_\_\_\_
  - a. It helps them to relax
  - b. Their friends or family vape
  - c. They like the taste of it
  - d. They think it is safer than tobacco cigarettes
  - d. All the above
8. I feel pressured to vape.
  - a. Yes
  - b. No
  - c. Sometimes

9. Effects that vaping has on my body are \_\_\_\_\_

- a. Decreased brain development
- b. Problems with breathing
- c. Increase heart rate
- d. Higher chance of developing cancer
- e. All the above

10. How likely are you to use vaping products?

- a. Not at all
- b. Not sure
- c. Very likely
- d. I already vape

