#### B. Thesis statement

1. 'To vape or not to vape' goal is to prevent students from vaping while also reducing the percentage that currently vape. Our program will accomplish this by providing education on what vapes are while also giving the short and long-term risk. ([name])

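### The only item on future vaping gives no time frame and includes a present-status answer, so vapers who choose that answer record no intention

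*Combined protocol and SAP*

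**What the plan says.** Section 1.2, objective 4: "To decrease the percentage of students who say that they are likely to vape in the future". The secondary hypothesis (the second paragraph numbered 1.4.1) likewise concerns the individual's "likelihood of vaping in the future".

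Current users are part of the target. Section 2.1.2 aims to "reduce the percentage pf the target population who are currently vaping", and the thesis statement in Appendix D gives the goal as to "prevent students from vaping while also reducing the percentage that currently vape".

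One item in Appendix C asks about likelihood of vaping. It is pre-test item 14, repeated word for word as post-test item 10: "How likely are you to use vaping products". Options a to c run from not at all, through not sure, to very likely. The fourth is "d. I already vape". The only other item that mentions the future (pre-test 7, post-test 3) is a true/false statement about smoking cigarettes.

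Current use is asked separately in pre-test item 2, option a: "Yes, I currently use these products". The post-test has no such item.

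Section 5.2 assigns McNemar's test to all categorical outcomes and gives no rule for reducing four answers to two.

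**The concern.** The item mixes two scales. Options a to c say what a student expects to do; option d says what the student does now. A vaper who ticks d has answered truthfully but has given no intention. At the post-test d is still true, including for someone the session has just persuaded to stop. Repeating it is honest, and it hides the change that objective 4 is meant to detect.

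The baseline is ambiguous too. Two vapers with the same behaviour and the same expectation of continuing can truthfully tick different answers, c and d. Without a coding rule, the percentage likely to vape depends partly on which they happen to tick.

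An intention not asked on the day cannot be recovered afterwards. The study is anonymous (section 3), and no later survey is described.

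**Working it through.** **1. The plan's own sample size.** Section 5.1 gives 35 for a Wilcoxon signed-rank test with dz = 0.5, 80% power and alpha 0.05. I used noncentral t power with N multiplied by the test's asymptotic relative efficiency (3/π, normal parent), two-sided. This gives N = 35 with power 0.801. Then 35 / (1 − 0.20) = 43.75, rounded up to 44. Both figures reproduce, but they concern a score outcome and say nothing about this item.

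**2. Time between the two answers.** In the section 3 program table, the components between pre-test and post-test last 3 + 5 + 3 + 5 + 3 + 5 = 24 minutes. A student who vapes at the first answer still does at the second.

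**3. What each answer pair does under three possible codings.** The plan specifies none of them. Options a and b are taken as not likely here.

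| Pre → post | Likely = c only | Likely = c or d | d set aside |
|---|---|---|---|
| d → d | no change | no change | excluded |
| d → a | no change | improvement | excluded |
| c → a | improvement | improvement | improvement |
| c → d | improvement, with no change in behaviour | no change | excluded |

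McNemar's test uses only discordant pairs. The d → d pair is uninformative in every column, so no later coding rescues it. The d → a pair counts only if d is coded as likely.

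**4. Baseline percentage.** Assume 100 students, 28 of them vapers, and 15% of the other 72 answering c (72 × 0.15 = 10.8). The 28% is section 1.1's figure for high school students; the 15% is my assumption. If all vapers tick d:
- c only: 10.8%
- c or d: 10.8 + 28 = 38.8%
- d set aside: 10.8 / 72 = 15%

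If instead all 28 vapers tick c, the c-only figure becomes 10.8 + 28 = 38.8%. That is a 28-point swing with identical behaviour. The figure with d set aside also becomes 38.8%. With c and d coded together it stays at 38.8% throughout.

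**5. Students able to show a change.** Assume every vaper ticks d both times. The number left is 100 × (1 − f), where f is the vaper share. Section 1.1 supplies 12% (high school, 2016), 28% (high school, 2019) and about 40% (kids who have ever tried vaping, so not a current-use figure).

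Power is for the exact two-sided McNemar test at 0.05. The number of discordant pairs is binomial (n, p10 + p01), and improvers among them are binomial with probability p10 / (p10 + p01). The shifts p10 (likely to not likely) and p01 (the reverse) are assumed.

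| f | Able to change | Power, 15% vs 2% | Power, 10% vs 2% |
|---|---|---|---|
| 0 | 100 | 0.90 | 0.56 |
| 12% | 88 | 0.84 | 0.49 |
| 28% | 72 | 0.74 | 0.38 |
| 40% | 60 | 0.63 | 0.28 |

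The first row is a fair comparison only if vapers would shift at the same rate as the others.

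**The case against.** The strongest reply is that the item is usable as it stands. Asking how likely someone is to use a product looks forward in ordinary English. Options a to c are open to everyone: the forms have no skip rule and no instruction that vapers must tick d. A vaper persuaded to quit can tick option a, and this does not contradict being a current user, because the stem asks about likelihood. If c and d are coded together as likely, that move counts as an improvement and the c-or-d ambiguity at baseline disappears. On this view much of the problem is a missing sentence in section 5.2. The item also works for non-users, whose prevention is an explicit aim. Section 2.1.2 approaches current users through knowledge, so the item answers mainly to objective 4 and the secondary hypothesis.

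Most of that stands, and it rules out two stronger readings that a reader might infer: that the item never asks about the future, and that current vapers are fixed at no change by the design of the form. The stem is implicitly prospective; what it lacks is a stated period. Vapers are locked at no change only if they tick d both times.

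The reply does not reach the vaper who ticks d twice. That answer is the most literal one for a current user, and no coding turns it into an intention.

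**Conclusion.** The point holds in a limited form. The sole item for objective 4 and the secondary hypothesis states no future period and places a present status on a likelihood scale. Vapers who choose d at both tests give no intention and contribute nothing to McNemar's test. The choice between c and d moves the baseline percentage unless the two are coded together.

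The size is not known from the documents. The 88, 72 or 60 students able to show change assume that every vaper ticks d twice, which is the worst case. The 28% is an outside high school figure, while this sample also includes middle school and college students. The 28-point swing should not be read as an expected error: it arises if d is not counted as likely, and then only at the extremes of the c/d split. The power figures rest on assumed shifts and show direction only.

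The change is worth making before the forms are used, because it is cheap and the lost information cannot be recovered later.

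**What to change.** On both forms, ask about a stated future period, for example the next 6 months, and delete option d. Section 2.2.1 mentions 6 months for a hoped-for fall in use across the DFW area, not as an individual's horizon, so it is a convenient choice and not one the plan dictates. Current use is already recorded by pre-test item 2.

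In section 5.2, define the McNemar outcome for this item, for example very likely or not sure versus not at all. Another two-level split would serve if it is fixed in advance and places the not-sure answer. Report the change separately for baseline current users (pre-test item 2, option a) and all others, so that continuing and starting are distinguished. This relies on the same pre/post linkage of forms that McNemar's test already needs.

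Cost: one reworded line and one deleted option on each form, and a short addition to section 5.2. The post-test would no longer repeat current status, which it records nowhere else. The revised forms and protocol text need IRB review under section 6.2.

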## **3. STUDY DESIGN**

The time frame for this study will be approximately one month, with the first presentation of the program being in March 2020. This program will be provided to high school and college students within the Dallas Fort Worth metroplex. The program will be implemented by community outreach, as the students will be presented with information about vaping and the resources necessary to prevent or stop vaping from their daily lives. The purpose of this study is to relay and publish data that will support the education of vaping and the many health risks associated with vaping products.

During this program, we will be presenting to 20 to 30 students at a time in a classroom setting, which will allow us to closely interact with participants. This is an anonymous study; therefore, all participants' names will not be listed nor stated in any documentation. In order to accurately complete this anonymously while also calculating our results, students will be asked to list their age, gender, race, and zip code on their survey. This program will be approximately 35 minutes. Participants will be given a pretest (Appendix C) before any information is presented. Students will be given an incentive to complete this program. Below is an outline (Appendix D) of the program:

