## **III. Main points**

1. Chemicals that are in vapes
2. The difference between e-cigarettes and vapes
3. Risk and side effects of vaping
4. What happens inside the body when vaping
5. Resources available to help quit and prevent vaping

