#### C. Main Points

1. Chemicals that are in vapes such as heavy metals (nickel, tin, and lead) ([name])
2. Explaining the difference between e-cigarettes and vapes. ([name])
3. What happens inside the body when vaping. ([name])
4. Giving the resources necessary to help stop students from vaping and preventing them as well. ([name])

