## **B. E-cigarettes vs. Vapes ([name])**

1. **Electronic cigarettes or better known as E-cigarettes**, are devices that look similar to traditional cigarettes and they are battery-powered device that works by heating a liquid into an aerosol that the user inhales and exhales. E-cigarettes do not contain tobacco. The e-cigarette liquid typically contains propylene glycol, nicotine, glycerin, flavorings, and other harsh chemicals. Nicotine is an addictive drug found in regular cigarettes and other tobacco products.
2. **Vape pens** consist of a rechargeable battery and refillable tank. The e-liquid in vaporizer products does not contain tobacco. The public makes it seem like vape products only have flavored water in them, which is not true! Vape products usually contain a propylene glycol or vegetable glycerin-based liquid with nicotine, flavoring and other harsh chemicals and metals.

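### The only paired measure of intention to vape uses an undefined term, 'vaping products', which some students may read more narrowly after the lesson

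*Combined protocol and SAP*

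**What the plan says.** Section 1.2 gives objective 4 as "To decrease the percentage of students who say that they are likely to vape in the future", and the secondary hypothesis (Section 1.4.1) says much the same. One item serves both. Pre-test item 14 and post-test item 10 in Appendix C ask "How likely are you to use vaping products" with the same four options: not at all, not sure, very likely, and already vaping. Neither form defines the term.

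The surrounding text differs between the two occasions:

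- **Pre-test only.** Item 2 asks "Do you or have you ever used a vape pen, e-cigarette, or other vaping products", which puts e-cigarettes under the general term. The post-test does not repeat pre-test items 1 to 4.
- **Order.** Section 3 states: "Participants will be given a pretest (Appendix C) before any information is presented". The lesson and the post-test follow in the same session.
- **Lesson outline.** Section 3 lists as a main point "The difference between e-cigarettes and vapes". Appendix D, I.C repeats it: "Explaining the difference between e-cigarettes and vapes".
- **Lesson body.** In Appendix D, II.B, e-cigarettes "are devices that look similar to traditional cigarettes and they are battery-powered device". The separate vape-pen paragraph says: "Vape products usually contain a propylene glycol or vegetable glycerin-based liquid with nicotine". Within II.B, 'vape products' appears only in the vape-pen paragraph.

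Section 5.2 assigns the McNemar test to categorical outcomes. It does not say how a four-option item becomes two categories.

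**The concern.** A before-and-after comparison measures change only if the question means the same thing both times. Here the wording is constant, but the context that gives it meaning is not. A student who intends to use e-cigarettes but not vape pens could answer 'very likely' under the wide reading at pre-test and 'not at all' under a narrow reading at post-test, both truthfully.

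Such a switch would count towards objective 4 and the secondary hypothesis. No other item on both forms asks about intention or use, so nothing else in the data could be used to check it. The forms are anonymous, so students cannot be asked afterwards what they understood.

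**Working it through.** **1. The plan's own figure.** The plan gives no figure for this item. The sample size in Section 5.1 is for a Wilcoxon signed-rank test with dz = 0.5. Taken as two-sided, with n multiplied by the relative efficiency 3/π and noncentral-t power, n = 35 gives power 0.801. Allowing for attrition, 35 / (1 − 0.20) = 43.75, which rounds up to 44. Both figures reproduce and are not in dispute. A wording change does not affect them.

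**2. Context of the item on each occasion.**

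| | Pre-test item 14 | Post-test item 10 |
|---|---|---|
| Stem and options | same | same |
| Definition on form | none | none |
| E-cigarettes named under the term on the form | yes, item 2 | no |
| Lesson contrast already heard | no | yes (Appendix D, II.B; recalled in the Conclusion just before the post-test) |

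The asymmetry is in the documents. Whether students act on it is not.

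**3. What a given number of switches would do.** This assumes 'very likely' and 'already vape' are grouped as likely, that k students switch from likely to not likely, and that none switch back. The exact two-sided McNemar p is 2 × 0.5^k:

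| k | p |
|---|---|
| 2 | 0.50 |
| 3 | 0.25 |
| 4 | 0.125 |
| 5 | 0.0625 |
| 6 | 0.031 |

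Section 5.2 does not say which version of the test is meant. The uncorrected chi-square version crosses 0.05 at k = 4 (p = 0.046). The continuity-corrected version crosses at k = 6 (p = 0.041).

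**4. What share of students that implies.** The documents give no baseline for this item. Section 1.1 quotes vaping rates of 12% and 28% among high school students, borrowed here as an assumed range. With the planned 100 students, m = 12 or 28 would give a likely answer at pre-test. Six switches would then be 6/28 = 21% or 6/12 = 50% of them.

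Let q be the assumed share of those m students who re-read the term narrowly, with no true change in intention. The expected fall is m × q points per 100 students. The chance of an exact p below 0.05 is P(X ≥ 6), with X binomial (m, q):

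| Baseline | q | Expected fall (points) | Chance of p < 0.05 |
|---|---|---|---|
| 12% | 20% | 2.4 | 2% |
| 12% | 40% | 4.8 | 34% |
| 28% | 10% | 2.8 | 5.5% |
| 28% | 20% | 5.6 | 50% |
| 28% | 30% | 8.4 | 89% |

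The result runs from negligible to decisive, depending on two quantities that the documents do not supply.

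**The case against.** The strongest reply is that the lesson never says e-cigarettes are not vaping products. Appendix D, II.B contrasts two kinds of device but gives them nearly the same contents and says neither contains tobacco. The sections on chemicals and on effects inside the body (II.A and II.C) speak of e-cigarettes and vapes together. Item 2 is fresh in memory: by the Section 3 timetable only 3 + 5 + 3 + 5 + 3 + 5 = 24 minutes separate the pre-test slot from the post-test. That timetable also has no slot for the contrast, although the Section 3 outline and Appendix D include it, so these should be reconciled. The students at risk are few: they must intend to use e-cigarettes and nothing else, take up the narrow meaning, and apply it. A current e-cigarette user would also have to stop counting that use as vaping.

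All of this stands, and it limits the likely size. It does not remove the difference in context between the two forms.

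A reader might go further and infer that the design has a built-in bias towards success, with p = 0.031 as its measure. The documents do not support that. Stressing shared contents and harms could widen the term for a student who had thought e-cigarettes were separate, which would push the answer the other way. The p of 0.031 is for six switches; two to five give 0.50 down to 0.0625. Nor can it be said that a comparison group would have exposed the problem: a group without the lesson could not separate re-reading from real change, since the lesson could cause both.

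**Conclusion.** The point holds as a possibility, and it is minor. The only paired measure of objective 4 and the secondary hypothesis uses an undefined term. The pre-test alone places e-cigarettes under that term, and the lesson in between draws a distinction that some students may carry into their second answer. A fall without a change in intention is plausible, but neither its direction nor its size is established.

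The illustrative figures rest on an assumed two-category split, no reverse switches, an assumed baseline and an assumed rate of re-reading. The case for acting is that the ambiguity is easy to remove beforehand and cannot be resolved from anonymous forms afterwards.

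**What to change.** Before the forms are used, give pre-test item 14 and post-test item 10 the same stem: *How likely are you to use a vape pen, e-cigarette, or other vaping product?* With the products named in the question, a separate printed definition is unnecessary. Adding a future time frame, to match objective 4, is a separate and optional change.

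The cost is a one-line edit on each form. Sample size, analysis and lesson stay as they are. If the edit is made after approval, Section 6.2 requires IRB review first. Section 10 lists $240 per document for review of subject materials ($312.00 with the 30% indirect cost) and $345 for an amendment without a revised consent form ($448.50). It does not say which fee would apply.

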## 5. STATISTICAL CONSIDERATIONS

## 5.1. Sample Size Considerations

A power analysis using the G-power 3.1 computer program (Faul & Erdfelder, 2009) indicated that a total sample of 35 people would be needed to detect a medium effect (Cohen's  $dz = 0.5$ ) with 80% power using matched-pairs Wilcoxon signed-rank test with alpha at 0.05 and assuming non-normal distribution. We need to enroll at least 44 subjects to account for 20% attrition rate. We plan to enroll 100 subjects in this study from whom we will collect pre- and post-test data on vaping.

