## 5.2. Statistical Analysis Plan

Descriptive analysis will be performed for all continuous variables. Mean  $\pm$  standard deviation will be presented for normally distributed variables and median  $\pm$  interquartile range will be presented for non-normal variables. Count and proportions will be presented for all categorical variables. All normally distributed continuous outcomes will be analyzed with paired t test and non-normally distributed continuous outcomes will be analyzed with nonparametric Wilcoxon signed-rank test. All Categorical outcomes will be analyzed using McNemar test.

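### The only intention item offers no 'likely' or 'unlikely' level, so a fall in the share of students likely to vape may be recorded only in part

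*Combined protocol and SAP*

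**What the plan says.** Section 1.2 sets as objective 4: "To decrease the percentage of students who say that they are likely to vape in the future". The secondary hypothesis, printed after the primary one in section 1.4.1, reads: "This program will decrease the individual's likelihood of vaping in the future".

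The item that serves both is number 14 on the Pre-Test and number 10 on the Post-Test in Appendix C. It asks "How likely are you to use vaping products", with four options on each form: (a) 'Not at all', (b) 'Not sure', (c) 'Very likely', (d) "I already vape". The question gives no time frame.

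No other post-test item measures intention to vape. Item 3 is a true/false statement about later cigarette smoking, and item 8 asks about feeling pressured. The pre-test questions on current use (items 1 to 4) are not repeated.

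On analysis, section 5.2 states: "All Categorical outcomes will be analyzed using McNemar test". It does not say which of the four options count as likely.

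**The concern.** Objective 4 counts a response level that the form does not offer. Between the lowest level and the strongest affirmative there is only 'Not sure', which expresses uncertainty and not a degree of likelihood. A student who thinks vaping somewhat likely and one who thinks it somewhat unlikely have no matching option. They can share 'Not sure' with students who really do not know, or round to an end.

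McNemar uses only pairs that change category. A student who goes from somewhat likely to somewhat unlikely and ticks 'Not sure' both times is a concordant pair and contributes nothing. At stake is whether a modest but real effect of a 35-minute session on intention would be seen, and whether a recorded change could be read as a change in the share likely to vape.

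Option (d) adds to this. It reports current use, not intention, so a current vaper who ticks it twice cannot report a lower intention.

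**Working it through.** **1. The plan's own figure.** Section 5.1 gives 35 pairs for dz = 0.5 at alpha 0.05, "with 80% power using matched-pairs Wilcoxon signed-rank test", and 44 after 20% attrition. Sidedness is not stated. Using noncentral-t power with n multiplied by the Wilcoxon efficiency 3/π, two-sided, n = 35 gives power 0.8007. Then 35/(1 − 0.20) = 43.75, rounded up to 44. Both figures reproduce. They use a generic effect size not tied to the intention item, so they neither support nor weaken this point.

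**2. Movement inside one box (assumed intentions).** Take 100 students, none in option (d): 60 definitely not, 20 probably not, 12 probably yes, 8 definitely yes. Six of the 12 move to probably not.

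- True share likely: 12 + 8 = 20% before and 6 + 8 = 14% after, a fall of 6 points.
- If both middle groups tick 'Not sure': before, 60 / 20 + 12 = 32 / 8; after, 60 / 26 + 6 = 32 / 8.
- 'Very likely' against the rest and 'Not at all' against the rest both give 0 discordant pairs. A signed-rank test on the ordered options sees only zero differences.
- With a separate 'likely' level there would be 6 one-way discordant pairs, exact two-sided p = 2 × 0.5^6 = 0.031.

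**3. Rounding, same students.** If the 12 tick 'Very likely' before, and after the session the 6 movers tick 'Not sure' while the other 6 stay at 'Very likely', the form shows 20% to 14%: the fall is recorded in full. If the 6 who have not changed their view also tick 'Not sure' afterwards, it shows 20% to 8%, a recorded fall of 12 points against a true 6.

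**4. General attenuation (assumed).** Take 100 pairs, 'Very likely' against other, no reverse movers, and an expected 10 students who truly move down from 'likely'. Let q be the share of 'likely' students who tick 'Very likely' at pre-test, the rest ticking 'Not sure'; all movers tick 'Not sure' or lower afterwards. The recorded fall is 10 × q points. With all discordant pairs one way, exact two-sided McNemar needs 6 (5 give 2 × 0.5^5 = 0.0625), so power = P(Binomial(100, 0.10q) ≥ 6).

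| q | Recorded fall (points) | Power |
|---|---|---|
| 0 | 0 | 0% |
| 0.25 | 2.5 | 4% |
| 0.5 | 5 | 38% |
| 0.75 | 7.5 | 77% |
| 1 | 10 | 94% |

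The last row is also what a scale with its own 'likely' level would record. For a true 5-point fall, power runs from 0% (q = 0) to 38% (q = 1); for 20 points, from 0% to about 100%. The form gives no information on q.

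**5. What the form still records.** If 10 of the 20 probably-not students in step 2 became definitely not, 'Not at all' against the rest would give 10 one-way discordant pairs, p = 2 × 0.5^10 = 0.002.

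**The case against.** The strongest reply is that the item is coarse but not blind. Moves from 'Not sure' to 'Not at all', and from 'Very likely' to anything lower, are recorded. The first kind satisfies the secondary hypothesis as worded. The session opens with a death linked to vaping and lists serious harms (Appendix D), so shifts to 'Not at all' are plausible. Likelihood of vaping is also not named among the outcomes in section 2.2. All of this stands, and it places the loss mainly on objective 4.

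A reader might infer more than the documents support:

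- *That affected students have no answer.* They can tick a neighbouring option. The result is misclassification, not necessarily missing data.
- *That the study will show no change, or that no analysis could show one.* Zero change requires every middle student to tick 'Not sure' both times and nobody to move into or out of the ends. Only movement inside 'Not sure' is beyond recovery.
- *That the baseline share likely is understated.* The direction depends on rounding; step 3 shows rounding up as well.
- *That the six-pair minimum for significance is a fault of this item.* It applies to exact two-sided McNemar on any scale.
- *That 'Not sure' must go.* Removing it would force undecided students, some as young as 12, to choose a side. That is a preference; the defect is the missing intermediate levels.

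None of this supplies the level that objective 4 counts.

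**Conclusion.** The point holds in a limited form. The sole measure of objective 4 and the secondary hypothesis has no 'likely' or 'unlikely' level. A real fall in the share likely can therefore be attenuated, in the extreme case to zero, or distorted by rounding. Changes that reach 'Not at all' or leave 'Very likely' are captured.

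The size of the loss cannot be computed from the documents, which give neither a response distribution nor any evidence on how students would round. The illustrative ranges above rest on assumed intentions, no reverse movers and nobody in option (d). That last assumption is favourable to the form: section 1.1 cites 28 percent of high school students using vaping products in 2019, and if a similar share attended, many could tick (d) twice.

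Choosing a cut for McNemar would settle which options count as likely, but would not separate the students who share 'Not sure'. This is a cheap improvement to the instrument, not a reason to regard the study as unable to detect any change in intention.

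**What to change.** Before first use, make the same changes on both forms:

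- Replace the options with one ordered, balanced scale that has explicit intermediate levels, for example very unlikely / unlikely / not sure / likely / very likely.
- Add a reference to the future to the question, to match objective 4.
- Drop option (d) and take current use from pre-test item 2, so that current vapers can also report a changed intention. Reading their change this way needs the same pairing of forms that McNemar already needs.
- State in section 5.2 that 'likely' plus 'very likely' count as likely for objective 4, with McNemar on that split.

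The cost is a slightly longer item on each form, with no extra students, and no comparability with any data collected on the present wording. If the forms have already been approved, section 6.2 requires IRB review of an amendment; section 10 lists $345 before indirect costs for one without a revised consent form.
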